### **3.1.1.1 Definition of Dose-Limiting Toxicity**

All adverse events, including DLTs, will be reported according to instructions in Section 5.3.5 and graded according to the NCI CTCAE v5.0, with the exception of CRS, which will be graded according to the Modified Cytokine-Release Syndrome Grading System (Appendix 9). DLTs will be treated according to clinical practice and will be monitored through their resolution. Any one of the following events will be considered a DLT if it occurs during the DLT assessment window (Days 1–14 of Cycle 1

for Arms A and B; Cycle 1, Day 8 to Cycle 2, Day 7 for Arm C) unless clearly attributed to another identified etiology by the investigator (e.g., cancer progression):

- Any Grade 4 or 5 adverse event
- Grade 3 febrile neutropenia lasting > 3 days
- Grade 3 elevation of serum hepatic transaminase (ALT or AST) lasting >7 days
  - Any Grade 3 AST or ALT elevation that occurs in the context of Grade  $\leq 2$  CRS (as defined by the criteria established by Lee et al. [2019]; see [Appendix 9](#)) and resolves to Grade  $\leq 1$  within < 3 days will not be considered a DLT.
- Grade 3 elevation of serum bilirubin (total)
- Any increase in hepatic transaminase (ALT or AST)  $> 3 \times$  baseline in combination with either an increase in direct bilirubin  $> 2 \times$  upper limit of normal (ULN) or clinical jaundice, in the absence of cholestasis or other contributory factors (e.g., concomitant exposure to known hepatotoxic agent, or documented infectious etiology)
  - This is suggestive of potential drug-induced liver injury (according to Hy's Law).
- Grade 3 non-hematologic, non-hepatic major organ adverse event, with the following exceptions:
  - Grade 3 nausea, vomiting, or diarrhea that improves to Grade  $\leq 2$  with standard-of-care therapy in  $\leq 3$  days will not be considered a DLT.
    - Grade 3 nausea or vomiting that requires total parenteral nutrition or hospitalization is not excluded and should be considered a DLT.
  - Grade 3 fatigue that improves to Grade  $\leq 2$  within 7 days will not be considered a DLT.
  - Grade 3 infection that resolves within 7 days to Grade  $\leq 2$  and does not require intensive care unit will not be considered a DLT.
  - Grade 3 fever (as defined by  $> 40^\circ\text{C}$ ) for  $\leq 48$  hours will not be considered a DLT.
  - Grade 3 laboratory abnormalities that are asymptomatic, resolve to Grade  $\leq 1$  or baseline within 7 days, and are considered by the investigator not to be clinically significant will not be considered a DLT.
  - Fractures of any grade at site of lytic bone disease will not be considered a DLT.
  - Grade 3 IRRs will not be considered a DLT, as generally IRRs are not considered to be dose-related events on the basis of experience with monoclonal antibodies. Precautions will be taken if IRRs Grade  $\geq 2$  occur (see Section [5.1.2.2](#)).
    - Grade  $\geq 4$  IRRs or re-occurrence of an IRR event in a patient that precluded the administration of the full dose or the administration of the next scheduled dose of study drug will be considered a DLT.

Anemia, neutropenia, lymphopenia, leukopenia, and thrombocytopenia are anticipated in the study population due to the extensive prior therapy and myeloma involvement in the R/R MM population (see Section 4.1). Investigator assessment of causality and change from pre-treatment baseline will be important to characterize the effect of RO7297089 on cytopenias. In addition, infection is a common occurrence in R/R MM due to prior therapy and hypogammaglobulinemia. Hence, infection that recovers as expected with appropriate therapy (as per above) will not be considered a DLT.

### **3.1.1.2 Dose-Escalation Rules**

The starting dose of RO7297089 will be 60 mg, administered IV weekly for Cohort 1.

Dose escalations will be guided by the mCRM-EWOC model ([Appendix 11](#)). The MTD is defined as the dose that maximizes the probability of a DLT being in the targeted toxicity interval in the range of 20%–35%, subject to the probability of the DLT being in the excessive toxicity interval in the range of 35%–100% being <25%. For each cohort, patients will be followed through a 14-day DLT assessment window. At each dose-escalation step, the dose can be escalated or de-escalated and/or an additional cohort at that same dose level could be enrolled. Refer to Section 3.1.1 for additional information. If MTD is not reached, the RP2D will be determined based on the totality of data including clinical activity, safety, PK, and pharmacodynamics biomarkers. Once the MTD or is RP2D determined, all patients in dose-escalation will be eligible to receive the RP2D, based upon ISC decision.

In addition, different dosing regimens (e.g., every 2 weeks) may be explored in parallel, if warranted, on the basis of the safety and PK profile of RO7297089, with DLT periods specific for each regimen and starting dose not exceeding the weekly MTD. Any evaluation of a different administration schedule will be based on the recommendation of the ISC and reviewed with study investigators. Addition of different dosing regimens will require a protocol amendment. For this new regimen, the mCRM-EWOC model and priors as defined in [Appendix 11](#), as well as the simulations, will be reviewed and possibly modified and the DLT assessment period will be extended to 21 days to ensure that patients have received at least two doses of study drug.

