### **3.1.4 Expansion Stage**

After dose escalation has been completed, approximately 30 patients will be enrolled in the expansion stage. Patients will be treated at the RP2D (at or below the MTD) to obtain additional safety, tolerability, and PK data, as well as preliminary evidence of clinical activity. The ISC will assess all safety data on an ongoing basis. At no time will the dose administered in the expansion stage exceed the highest dose level that qualified as an MTD in the dose-escalation stage.

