### Modified Continuous Reassessment Method with Escalation with Overdose Control Design

Details of the mCRM-EWOC design used in the study are described in this appendix. In addition, the design operating characteristics are evaluated through comprehensive simulations in this section. In this study, the MTD is defined as the dose maximizing the posterior probability that the DLT rate belongs to [0.20,0.35], while keeping the probability of overdose below 0.25. The details of the mCRM-EWOC design will be described below. Calculations are done using R package crmPack 0.1.9 (<https://cran.rproject.org/web/packages/crmPack/index.html>).

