#### **Dose-Response Model**

The probability of DLTs over doses (dose-DLT response curve) will be described by a two-parameter logistic regression model:

$$\text{logit}(p(d)) = \alpha + \beta \left( \frac{d}{d^*} \right)$$

where  $p(d)$  stands for the DLT rates under a dose level  $d$ , and  $d^*$  is set to 1200 mg in the study as the reference dose. Thus, the dose-DLT response curve follows a sigmoidal shape and can be flexibly adjusted by a parameter

$$\theta = \begin{pmatrix} \alpha \\ \log \beta \end{pmatrix} \sim N(\mu, \Sigma)$$

It is common to assume such a sigmoidal curve since usually the DLT rate increases monotonically while dose levels go up, but not in a linear way because it has a minimal level 0 and will reach a plateau when dose is very high. It is anticipated that RO7297089 would have a similar dose-DLT relationship.

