### **Stopping Rules**

The dose-escalation trial will continue until the recommended Phase II dose (RP2D) has been determined or the maximum sample size of ~40 is reached or pre-specified precision rules have been fulfilled:

- At least 9 patients have accrued overall;
- At least 6 patients have been accrued near the MTD dose where “near” is defined as being within 20% of the MTD;
- The probability that the MTD lies within the target toxicity interval is above 40%.

The Sponsor in consultation with the Investigators may decide to stop the escalation prior to above stopping criteria are met if the RP2D has been determined.

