**Simulations**

A simulation study is conducted to evaluate the operating characteristics (sample size, estimated MTD, number of patients treated, overdose, etc.) for the chosen design parameters (priors, reference dose, stopping rules).

Scenarios with different toxicity profiles are simulated with hypothetical MTDs from 60 mg (low MTD) to >1650 mg (illustrating a scenario for which no toxicities are expected). The dose grid in simulations is set as 60 mg to 100 mg by 5 mg as a unit followed by increments of 10 mg all the way up to 1650 mg. The starting dose is 60 mg. Simulations are conducted based on 3-patient cohorts throughout the entirety of the study.

Figure 2 “True” Scenarios Used for Simulations

Each scenario uses 1000 simulated trials, analyzed by generating a MCMC chain run for 15000 iterations following a 5000-iteration burn-in period. Every one out of 2 iterations are saved after the burn-in i.e., step=2. Random manual checks revealed no significant MCMC convergence issues using standard convergence diagnostics.

The design is evaluated using the following criteria: the MTD chosen, the number of subjects treated at doses higher than the MTD and the sample size of the trials. The following table demonstrates the simulation study result.

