**Table 3 Operating Characteristics of the mCRM-EWOC Design with Respect to the Chosen Scenarios**

Scenario	Target Dose Interval in True Scenario (mg)	mCRM-EWOC			
		Overall N of Patients	N Patients Treated above Target Toxicity Interval	Proportions of DLTs in the trials	Doses selected as MTD (mg)
1	100 - 180	15 (9, 21)	5 (0, 12)	27.8% (22.1%, 33.3%)	146.2 (80, 210)
2	210 - 350	17 (12, 24)	4 (0, 9)	23.4% (16.7%, 28.6%)	258 (160, 410)
3	400 - 580	19 (15, 24)	3 (0, 9)	20.1% (16.7%, 25%)	440.9 (270, 601)
4	630 - 840	21 (15, 27)	5 (0, 9)	18.8% (14.2%, 23.8%)	647 (420, 960)
5	940 - 1150	22 (18, 27)	4 (0, 6)	16.8% (12.5%, 20.8%)	949.4 (620, 1370)
6	1250 - 1450	22 (18, 27)	5 (3, 9)	14.6% (11.1%, 18.5%)	1299.8 (900, 1640)
7	1700 - 1850	34 (18, 42)	0 (0, 0)	10.3% (4.8%, 14.3%)	1622.7 (1550, 1650)
8	159 - 421	17 (9, 24)	3 (0, 9)	23.8% (16.7%, 33.3%)	263.7 (110, 470)

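### The MTD rule has no floor and *MTD not reached* is never defined, so on the Appendix 11 grid the rule labels the top dose an MTD even when no DLTs occur

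*Combined protocol and SAP*

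**What the plan says.** - **Definition.** Section 3.1.1.2: "The MTD is defined as the dose that maximizes the probability of a DLT being in the targeted toxicity interval", with the interval set at 20%–35%. Appendix 11 makes clear that this is a posterior probability for the DLT rate, maximised "while keeping the probability of overdose below 0.25".
- **Fallback.** The same section continues: "If MTD is not reached, the RP2D will be determined based on the totality of data". Neither this section nor any other says what makes an MTD not reached.
- **Precision criteria.** Section 6.4 (Primary Safety Model) and Appendix 11 (Stopping Rules) require at least 9 patients overall, at least 6 within 20% of the MTD, and a third condition: "The probability that the MTD lies within the target toxicity interval is above 40" percent. These are conditions for ending escalation. Escalation may also end at about 40 patients, or once the RP2D is considered defined, without meeting them.
- **Simulations.** Appendix 11 runs the dose grid to 1650 mg and describes the case of an MTD above 1650 mg as "illustrating a scenario for which no toxicities are expected". Table 3, scenario 7 (true target interval 1700–1850 mg), gives selected MTD 1622.7 mg (1550, 1650), 34 patients (18, 42) and 10.3% DLTs.
- **Expansion.** Section 3.1.4: "At no time will the dose administered in the expansion stage exceed the highest dose level that qualified as an MTD" in the escalation stage.

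**The concern.** A maximiser with no minimum returns a dose whenever at least one dose satisfies the overdose limit, however small the maximised probability is. If the drug causes few or no DLTs, the rule settles on the highest dose available to it and calls it the MTD. That label means a DLT rate of 20%–35%, while the model that produced it may be nearly certain that the rate is below 20%.

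The case is realistic for this drug. Section 1.2 reports no adverse findings in monkeys up to 50 mg/kg. Section 1.3 reports that the related CD16a bispecific did not reach an MTD. Section 3.1.1.1 excludes most Grade 3 infusion-related reactions from the DLT definition.

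Estimating the MTD is part of the primary objective (Section 2.1). If the definition is applied literally, the label is wrong. If the Internal Safety Committee (ISC) instead decides by judgment that no MTD was reached, the Section 3.1.4 ceiling, which refers to a dose that qualified as an MTD, has nothing to refer to.

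**Working it through.** **Inputs (Appendix 11).** Reference dose 1200 mg; prior mean (0.2098152, 0.7905444); prior variances 2.3807734 and 0.07025577, covariance 0.3267589; grid 60–100 mg by 5, then by 10 to 1650 mg; cohorts of 3; maximum 3-fold step; cap about 40, which is 42 in cohorts of 3.

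**Rule.** Selected dose = argmax over d of P(0.20 ≤ p(d) ≤ 0.35 | data), subject to P(p(d) > 0.35 | data) < 0.25 and the 3-fold limit. Posteriors were obtained by numerical integration over the bivariate normal prior.

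**Model reading.** The printed form, linear in d/1200 with a log-normal slope, gives a prior probability of 77% that the DLT rate at 60 mg exceeds 30%. Appendix 11 says this should be very unlikely. A model in log(d/1200) with a normal slope comes closest to the appendix tables and is the main reading here. The printed form serves as a sensitivity check.

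**Reproducing the plan's figures.**
- Table 1, next dose with no DLTs: 60→180 (plan 180), 180→510 (500), 500→1270 (1180), 1180→1650 (1600), 1600→1650 (1650). The match is approximate.
- Table 3, scenario 7, 400 simulated trials. The true curve is assumed logistic in log dose with p(1700) = 0.20 and p(1850) = 0.35. Results: mean MTD 1617 mg (plan 1622.7), N 32.1 (plan 34), DLTs 10.3% (plan 10.3%). The lower quantile for the MTD is 1360 mg (plan 1550).

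**Zero DLTs throughout, log-dose reading.** The rule returns 1650 mg from N = 12 onward:

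| N | P(20%–35%) at 1650 mg | P(<20%) | P(>35%) |
|---|---|---|---|
| 12 | 0.238 | 0.646 | 0.117 |
| 18 | 0.097 | 0.893 | 0.010 |
| 24 | 0.031 | 0.968 | 0.001 |
| 39 | 0.001 | 0.999 | 0.000 |

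At N = 39, P(20%–35%) is 0.14% on this reading. It is 0.5% under the printed linear form and 0.5% under log dose with a log-normal slope. All three select 1650 mg, with P(<20%) about 99.5% or more. At no step does P(20%–35%) exceed 0.30, so the 40% criterion is never met.

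A check that uses no model: on this path the first 12 patients are below 1650 mg, so 39 − 12 = 27 are treated there. If the true rate were 20%, the chance of no DLT among them would be 0.8^27 ≈ 0.0024.

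**Scenario 7 analogue.** All 400 trials return an MTD, although every grid dose is below target. Of these, 178 (178/400 = 44.5%) stop at the maximum sample size without meeting the precision criteria, and in 55.2% the selected dose has P(<20%) above 0.5.

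**Scenario coverage.** The DLT proportion of 10.3% in scenario 7 is the lowest of the eight in Table 3. No scenario therefore represents absence of toxicity, and no *not reached* outcome is tabulated.

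**The case against.** A reader might infer that the *not reached* clause can never operate, or that the definition closes off the totality-of-data route to the RP2D. The documents do not support either reading.

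- Section 3.1.3 speaks of the MTD being declared, so it is a decision. Section 6.4 and Appendix 11 let clinical judgment override the model in dose selection. No text obliges the sponsor to report the maximiser as the MTD. The clause is undefined, and the ISC could still invoke it.
- Section 6.4 and Appendix 11 allow escalation to end because the RP2D has been determined from several kinds of data. That route does not depend on MTD status.
- 1650 mg is the edge of a grid stated for the hypothetical trials and simulations. The protocol body sets no top dose, and Table 2 recommends 40 and 25 mg, below the grid's lower end. Without the upper edge, the zero-DLT maximiser after 18 patients is of the order of 16,000 mg, an extrapolation far above any tested dose. That could fairly be read as *not reached*.
- The no-DLT escalation path is worked through in Table 1. Only its end-of-trial classification is missing.
- The 40% criterion is a weak filter near the boundary. In the scenario 7 analogue 222 of 400 trials (55.5%) still meet it. At least 55.2% − 44.5% = 10.7% meet it while P(<20%) exceeds 0.5.

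All of this stands, and it limits the point to declaration and labelling. It does not remove the point. The override provisions concern dose selection and do not say when an MTD has been reached. On the only grid for which operating characteristics are given, Table 3 itself reports an MTD where none exists on the grid.

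**Conclusion.** The concern holds as a defect in how the MTD result is declared. The definition has no floor, *MTD not reached* has no criterion, and on the Appendix 11 grid the stated rule gives 1650 mg the MTD label at a posterior target probability of about 0.1%–0.5% after 39 patients with no DLTs. That result comes out the same under all three model readings tried. It assumes that the grid ends at 1650 mg, that cohorts are of 3, and that escalation continues to about 40 patients; an earlier RP2D-based stop would leave a less extreme posterior (9.7% at N = 18 on the log-dose reading).

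The scenario 7 percentages are less secure. They rest on an inferred parameterisation and an assumed true curve. The tabulated 1622.7 mg, by contrast, is the plan's own figure. Because the point decides how a primary-objective result is stated, it should be settled before escalation ends.

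**What to change.** In Sections 3.1.1.2 and 6.4 and in Appendix 11, state that:

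1. The selected dose is declared the MTD only if the posterior probability of a DLT rate of 20%–35% at that dose exceeds 40%, the plan's existing precision criterion.
2. If it does not, and P(DLT rate <20%) dominates at the highest dose evaluated (the sponsor to fix the threshold, for instance above 50%), the result is *MTD not reached*, reported with that dose and the probabilities of under-, on- and over-target rates.
3. Remaining cases, including those with no admissible dose, are reported as *MTD not determined*.

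Report the three probabilities with any declared MTD as well, since 40% is a modest floor. Re-tabulate Table 3 with the proportion of trials ending *not reached*, add a 0% DLT scenario, and correct the description of the above-1650 mg scenario, which has 10.3% DLTs. Section 3.1.4's ceiling must be reconciled with the case in which no dose qualified as an MTD.

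The cost is a few sentences and a simulation re-run, with no extra patients. Trials whose true MTD lies just above the grid will more often report no MTD (44.5% in the scenario 7 analogue). Within range the loss is negligible: in analogues of scenarios 1, 3 and 6, every trial that returned a dose met the criteria (378, 400 and 400 of 400; the other 22 in scenario 1 had no admissible dose at or above 60 mg).

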### **3.1.2 Continued Dosing Beyond the Dose-Limiting Toxicity Observation Period (Cycles ≥2)**

Nonclinical toxicology data supports RO7297089 treatment every 7 days. The ethical conduct of a clinical study of cancer requires that patients have the opportunity to continue study treatment provided that the treatment is active and tolerable and patients comply with protocol requirements. Therefore, dosing beyond Cycle 1 for patients with R/R MM will be allowed in the absence of unacceptable toxicity or objective evidence of disease progression as assessed by the treating study investigator and following a careful assessment and discussion of the potential risks and benefits with the patient. Patients will *continue study treatment* until objective disease progression is documented or unacceptable toxicity, whichever occurs first.

RO7297089 administration will be interrupted in patients who experience a DLT during the DLT assessment window (Section 3.1.1). Patients who experience a DLT during the first cycle and whose toxicity returns to baseline within 14 days may be restarted at a dose level tolerated by the prior cohort following discussion with the Medical Monitor. A treatment delay beyond 14 days may be acceptable upon discussion with the Medical Monitor (see Section 5.1.2).

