### **Continued Dosing Beyond the Dose-Limiting Toxicity Observation Period (Cycles $\geq 2$ )**

Nonclinical toxicology data supports RO7297089 treatment every 7 days. The ethical conduct of a clinical study of cancer requires that patients have the opportunity to continue study treatment provided that the treatment is active and tolerable and patients comply with protocol requirements. Therefore, dosing beyond Cycle 1 for patients with R/R MM will be allowed in the absence of unacceptable toxicity or objective evidence of disease progression as assessed by the treating study investigator and following a careful assessment and discussion of the potential risks and benefits with the patient. Patients will *continue study treatment* until objective disease progression is documented or unacceptable toxicity, whichever occurs first. RO7297089 administration will be interrupted in patients who experience a DLT during the DLT assessment window. Patients who experience a DLT during the first cycle and whose toxicity returns to baseline within 14 days may be restarted at a dose level tolerated by the prior cohort following discussion with the Medical Monitor. A treatment delay beyond 14 days may be acceptable upon discussion with the Medical Monitor.

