### **5.1.2 Management of Patients Who Experience Adverse Events**

#### **5.1.2.1 Dose Modifications and Interruptions**

All considerations of dose and schedule modifications should be discussed with the Medical Monitor. The following guidelines regarding dose and schedule modifications should be followed:

- In general, patients receiving RO7297089 who experience a Grade 4 non-hematologic adverse event that is not considered by the investigator to be attributable to another clearly identifiable cause should permanently discontinue all study treatment. However, for patients with Grade 4 adverse events of asymptomatic laboratory changes, study treatment may be resumed upon resolution to Grade  $\leq 1$  or baseline with approval of the Medical Monitor.
- For patients who experience IRRs with the first dose of RO7297089, or are at increased risk of recurrent IRRs with subsequent doses, the infusion rate may be slowed by 50% (Section [5.1.2.2](#)). Modifications to infusion rate in these circumstances should be discussed with the Medical Monitor.
- In general, patients who experience either an adverse event that meets the definition of a DLT or other Grade 3 adverse event that is not considered by the investigator to be attributable to another clearly identifiable cause (e.g., documented disease progression, concomitant medication, or pre-existing medical condition) will be allowed to delay dosing for up to 2 weeks (or longer if approved by the Medical Monitor) in order to recover from the toxicity. Patients may continue to receive additional infusions of RO7297089, provided that the toxicity has resolved to Grade  $\leq 1$  (or for laboratory abnormalities, return to  $\geq 75\%$  of the baseline value), within 2 weeks.

- A reduced dose for subsequent infusions of RO7297089 should be considered and discussed with the Medical Monitor. Decisions on continued treatment following a DLT or other study treatment–related Grade 3 toxicity should be made following a careful assessment and discussion of risk versus benefit with the patient by the investigator and approval of the Medical Monitor, including in the following scenarios:
  - Patients with Grade 3 or 4 event of anemia if manageable by red blood cell transfusions as per institutional practice may continue without dose reduction with approval of the Medical Monitor.

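### Sections 3.1.2 and 5.1.2.1 give different restart terms for the same first-cycle DLT, and no text says which governs

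*Combined protocol and SAP*

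**What the plan says.** Section 3.1.2 interrupts dosing for any DLT in the assessment window. For a DLT in the first cycle it then gives restart terms: a patient "whose toxicity returns to baseline within 14 days may be restarted at a dose level tolerated by the prior cohort", once this has been discussed with the Medical Monitor. The synopsis repeats the rule ("may be restarted at a dose level tolerated by the prior cohort").

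Section 5.1.2.1 deals with the same events. Its third guideline begins "In general, patients who experience either an adverse event that meets the definition of a DLT or other Grade 3 adverse event", limited to events without another clear cause, and allows a delay of up to 2 weeks, or longer with Medical Monitor approval. On recovery it says "Patients may continue to receive additional infusions of RO7297089, provided that the toxicity has resolved to Grade" 1 or lower, "or for laboratory abnormalities, return to" at least 75% of the baseline value, within 2 weeks. On dose it says "A reduced dose for subsequent infusions of RO7297089 should be considered and discussed with the Medical Monitor". Continuing after a DLT needs an assessment of "risk versus benefit with the patient by the investigator and approval of the Medical Monitor".

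Section 5.1.2.1 also has special cases. Grade 3 or 4 anemia, thrombocytopenia or neutropenia that can be managed with transfusion or G-CSF may continue without dose reduction if the Medical Monitor approves. Grade 4 non-hematologic events generally mean permanent discontinuation, except that "for patients with Grade 4 adverse events of asymptomatic laboratory changes, study treatment may be resumed upon resolution to Grade" 1 or lower, or to baseline, again with approval.

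**The concern.** This is a first-in-human study. A patient who has just had a DLT is the patient for whom the re-dosing rule matters most. One section ties restart to full recovery and to a dose that the previous cohort tolerated. The other leaves room to resume with residual toxicity, and at the dose that caused the event. Section 4.3.2 sends sites to Section 5.1.2.1, the looser text, for dose modification after adverse events. Two sites, or the same Medical Monitor on two occasions, could treat the same event differently and each cite the protocol.

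**Working it through.** No formula or plan figure is involved. The check sets the two texts side by side, looks for a rule that ranks them, and tests the wording against the DLT definition and window.

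**Terms for a first-cycle DLT**

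| | Section 3.1.2 and synopsis | Section 5.1.2.1 |
|---|---|---|
| Recovery needed | Baseline | Grade 1 or lower; for laboratory values, at least 75% of baseline |
| Time allowed | 14 days; longer after discussion | 2 weeks; longer with approval |
| Restart dose | A level the previous cohort tolerated | Reduction to be considered; no level named |
| Medical Monitor | Discussion | Approval, with risk-benefit assessment |

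The sections agree on timing and on involving the Medical Monitor. They differ on recovery level and restart dose.

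**Two cases**

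1. A patient has no toxicity at baseline, then a Grade 3 DLT that has improved to Grade 1 when 14 days have passed. The Section 3.1.2 condition is not met. The Section 5.1.2.1 condition is met, and resumption at the same dose is open if approved.
2. A patient is back at baseline within 14 days. Section 3.1.2 points to the previous cohort's tolerated dose. Section 5.1.2.1 asks only that a reduction be considered.

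**Where the two diverge.** Mainly Grade 3 DLTs. Manageable cytopenias have their own exceptions in Section 5.1.2.1, and infusion-related reactions and CRS have their own tables. For Grade 4 non-hematologic events Section 5.1.2.1 is the stricter text, because Section 3.1.2 has no discontinuation rule.

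**Search for precedence.** Section 3.1.2 refers to Section 5.1.2 only for delays beyond 14 days. Section 3.3.3 names Sections 3.1 and 5.1.2 together without ranking them. Sections 4.3.2 and 4.3.2.1 point to 5.1.2.1 and 5.1.2. Section 4.5 requires acceptable clinical and laboratory findings before each dose but does not define acceptable. None of these settles the question.

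**Laboratory criterion.** At least 75% of baseline is a floor, which suits values that fall. Section 3.1.1.1 names rises as DLTs: ALT or AST above 3 times baseline with raised direct bilirubin or jaundice, prolonged Grade 3 ALT or AST, and Grade 3 bilirubin. For these the criterion states no upper limit. Section 5.1.2.1 already has suitable wording (Grade 1 or lower, or baseline) for Grade 4 asymptomatic laboratory changes.

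**Arm C.** Section 3.1.1 sets the window from Cycle 1, Day 8 to Cycle 2, Day 7: 7 days in Cycle 1 (Days 8 to 14) plus 7 in Cycle 2 (Days 1 to 7), 14 in all. Half of the window therefore lies outside the first cycle, and the Section 3.1.2 restart terms do not reach it.

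**Prior cohort.** Cohort 1 (60 mg) has none. Section 3.1.1.2 also lets a dose level be repeated or lowered, so the previous cohort need not have had a lower dose. In the hypothetical Table 2 of Appendix 11, one DLT in three patients at 180 mg leads to 180 mg again.

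**The case against.** The best defense is that Section 5.1.2.1 is worded as general guidance while Section 3.1.2 is specific to a first-cycle DLT, so the specific rule prevails. A patient restarted at baseline on the previous cohort's tolerated dose also satisfies both sections. This reading is natural, but the protocol does not state it, and Section 5.1.2.1 expressly names DLTs without excepting Cycle 1.

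The safeguards are real. The Medical Monitor is involved on both routes, and Section 4.5 requires a toxicity check before every dose. Section 5.1 limits dosing beyond Cycle 1 to patients without unacceptable toxicity, and similar toxicity recurring at a reduced dose means discontinuation. These limit the harm. They do not tell the Medical Monitor which recovery level or dose applies.

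A reader might infer four stronger points that the documents do not support:

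- *Section 3.1.2 is an exclusive rule.* It says what may be done; exclusivity is an inference, although baseline recovery and the prior-cohort dose are its stated terms.
- *The 75% criterion permits dosing during an active liver DLT.* The text speaks of a return toward baseline, and Section 4.5 would stop dosing on unacceptable values. The defect is the missing upper limit.
- *Section 3.1.2 could send a patient to a higher dose after a de-escalation.* The word tolerated makes that doubtful; the wording is only unclear.
- *The size of the escalation step measures the harm.* It does not show how often the sections diverge or with what result.

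**Conclusion.** Wrong as written: an internal inconsistency that bears on patient safety. The two sections set different recovery levels and restart doses for the same first-cycle DLT, and nothing in the current text ranks them. The laboratory criterion does not fit increases, and the first-cycle wording omits half of the Arm C window.

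The size cannot be estimated. The documents report no DLT, and the affected group is mainly patients with a Grade 3 DLT who either keep residual Grade 1 toxicity above baseline or are proposed for restart at the same dose. A reader might also infer that the dose-finding is compromised. It is not: restart comes after the DLT has been counted, so DLT counts, the model and the MTD estimate do not change.

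The conclusion assumes that no document outside the protocol, such as a site manual, already states which section governs.

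**What to change.** 1. In Section 5.1.2.1, state that the Section 3.1.2 restart terms apply to DLTs in the DLT assessment window. Keep the listed cytopenia exceptions and the Grade 4 discontinuation rule. At 60 mg, where there is no prior cohort, require a reduced dose agreed with the Medical Monitor, or discontinuation.
2. In Section 5.1.2.1, limit the 75% criterion to laboratory decreases, and require Grade 1 or lower, or baseline, for increases. This is still needed after change 1, because Section 5.1.2.1 would continue to govern laboratory events outside the window.
3. In Section 3.1.2 and the synopsis, refer to the DLT assessment window instead of the first cycle. Clarify that the prior cohort's tolerated dose means a cleared dose below the one at which the DLT occurred.

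The cost is wording in Section 3.1.2, Section 5.1.2.1 and the synopsis, with no change to procedures, sample size or model. A few patients would wait longer or restart at a lower dose. The existing option of a delay beyond 14 days after discussion with the Medical Monitor remains.
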